**Table 4. Proposed Study Mediators**

Self-Efficacy for Diet & Exercise	
 
• 12 items assess exercise SE
 
• 20 items assess eating SE (Sallis et al., 1988; Watters, Satia, and Galanko, 2007).
 

Social Support for Eating & Exercise	
 
• Respondents rate frequency of comments from friends/family on respondent's efforts to change dietary or exercise habits.
 
• Measure has good internal consistency with Black populations (Sallis et al., 1987; Ammerman et al. 2002).
 

Treatment Self-Regulation Questionnaire	
 
• assesses autonomous/intrinsic motivation and controlled/extrinsic motivation for weight loss (Ryan and Deci, 2000; Fuemmeler et al., 2006).
 

**Process Measures**

**Attrition from Measurement.** We will maximize retention by providing *cash incentives and lotteries* for each posttest. **We will conduct posttest measurement at study sites located in participant neighborhoods and will offer to do posttests over the phone or in participants' homes if necessary. We will identify a core set of primary and secondary outcomes that interviewers can prioritize.** We will document all attrition from measurement using a brief instrument that addresses maintenance of exercise, weight, and reasons for refusal, **and we will maximize the utility of available data using analytic techniques described in the analysis section. [name] has extensive experience retaining participants in weight loss trials and has retained more than 90% at 18 months ([name] et al, 2010)**

**Process Evaluation.** Process evaluation allows investigators to assess intervention implementation (Campbell et al. 2007; Glasgow et al. 2001). The RE-AIM framework uses five dimensions (reach, efficacy or effectiveness, adoption, implementation, and maintenance), (Glasgow, Vogt, and Boles, 1999) to evaluate the implementation of interventions (Glasgow et al., 2001). Measures that we will use are shown in Table 5.

**Table 5. RE-AIM Process Evaluation Framework for Fit and Strong and Fit and Strong Plus**

Reach (participation)	Implementation (dose and fidelity)

 
• # of participants completing Fit and Strong! sessions
 
• # of participants completing Fit and Strong! Plus sessions
 
• Age, education, race/ethnicity of participants
 
• % of eligibles in site catchment area (census data)
 
	
 
• Attendance
 
• Instructor attrition
 
• Site visit evaluations in Week 4 using systematic checklist
 
• Instructor listserv and hotline staffed by PIs and dietitian
 
• Participant/Instructor program evaluations (Appendix I)
 

Efficacy Changes at 2 and 6 months in mediators, dietary, weight loss, and OA symptom change outcomes	Maintenance • Maintenance of change at 12 and 18 months in mediators, dietary, weight loss, and OA symptom change outcomes Follow-up interviews with participants, instructors and Park District managers to assess sustainability
Adoption • Perceived barriers to implementing Fit and Strong Plus • # of participants in Fit and Strong Plus using weight loss maintenance strategies (e.g., self-monitoring, problem solving, stimulus control, regular physical activity) – subset of questions in Diet TR calls	

**Data Management**—All survey forms will be designed using REDCap. Project staff will enter data into REDCap during data collection, and data will be automatically uploaded for processing. Data will be stored in univariate form. We will use Stata's "reshape" command to reformat to multivariate form if necessary. We will run standard checks for outliers, duplicates, and other errors common to complex data entry and processing. All missing data will be flagged, and we will develop routines for imputations of missing data where the proportion of missing data is small. More complex imputation strategies will be developed if warranted. All data files will be password protected, and hard copies of questionnaires will be stored in locked cabinets in the research office.

**Data Analysis**—The basic trial design consists of one between-participant effect (customary Fit and Strong! vs. Fit and Strong! Plus) and one within participant effect (time) variable. Although the structure of the study is factorial, data analysis will be based on the general linear mixed model in a regression format (this approach is

more flexible than traditional ANOVA). Because the same persons will be measured repeatedly, the conventional regression assumption regarding independence of error terms is untenable. There are two ways to deal with this problem: generalized estimating equations (GEE) and random effect models. GEE is simpler but requires more power and a stronger set of assumptions regarding missing data. Random effect models can be used to analyze longitudinal data and permit a more sophisticated approach to analyses than GEE at the cost of some additional complexity. The basic model for data analysis is

$$Y_{it} = \beta_0 + \beta_1 Plus_i + \beta_2 Time_{it} + \beta_3 Plus_i * Time_{it} + \beta_4 ARA_i + u_i + e_{it}$$

where  $Y_{it}$  represents a particular outcome variable for person  $i$  at time  $t$ , *Plus* is a dummy variable for the Fit and Strong! Plus effect, relative to customary Fit and Strong!, *Plus\*Time* represents the interaction with time, *ARA* is a covariate,  $u_i$  is the random effect for person  $i$  and  $e_{it}$  is a person-time specific error term. The *Plus\*Time* interaction tells us whether the rate of change with respect to time is greater (or less) in the Plus condition compared to customary Fit and Strong!. As shown, the model is for a continuous outcome, but it can be estimated for a wide variety of outcome variables (e.g., logistic regression and ordered logistic regression models). Time can be represented in multiple ways in addition to the simple linear effect shown here. By including the square of time we can test whether the effects of time are non-linear, and by including properly coded dummy variables for discrete time, we can test more specific hypotheses regarding non-linear effects. A crucial assumption of such models is that the person-specific error term,  $u_i$ , is uncorrelated with the remaining variables, which is plausible given the randomized design. The model, as written, assumes an “exchangeable” correlation matrix among the errors. However that assumption can be relaxed by using simple auto-regressive or Toeplitz (banded) correlation structures. All analyses will be done using Stata.

Analyses of secondary outcomes will examine the magnitude of between and within group differences at all time points to determine whether the addition of a diet component to Fit and Strong! benefits these outcomes (as expected) or is neutral or harmful with respect to certain outcomes. Exploratory analyses will evaluate movement on the new readiness for total joint replacement measure, and will examine patterns and trends in healthcare utilization, healthcare cost, and quality of life between and within the two study groups.

**Missing Data.** Because we use longitudinal covariates to control on items like pain, in many cases missing data can be treated as “ignorable,” meaning that dropout will be missing at random (MAR) conditional on covariates and prior state. However, we will use “pattern mixture models” (Little, 1993; Hedeker and Gibbons, 1997) to explore the sensitivity of estimates to missing data assumptions. Specifically, we will include the observation pattern for each case in the model via dummy variables, interact those dummies with design variables, and compute a weighted average of the effects for the design variables based on the missing data problems. This method will allow us to assess what the effects of the design variables would have been, had all participants remained in the study.

**Power Analysis.** Based on prior work ([name] et al., 2010), we used software developed by Hedeker et al. (1999) to obtain sample size estimates. Assuming a 2-tailed test, a relatively small effect size of .2 (based on a five percent end point difference in mean weight and a linear pattern of change over time), 5% attrition at each time point, and a cross time correlation for weight of .9, we find that we need a sample size of approximately 300 subjects to detect an effect size of .2 (a 5% reduction in weight) at the end of the study with power = .9. In general, power estimates of this kind are not strongly affected by assumptions regarding attrition. However, we will enroll **400** subjects in order to maximize power.

**Timeline.** The timeline outlining all activities associated with the project is shown in Appendix C. It demonstrates that we will be able to achieve all of the tasks described within the **5**-years of the study.

**Methodological Considerations.** The proposed study has many strengths, including a large sample of high-risk older adults, an innovative integration of evidence-based weight loss approaches with Fit and Strong!, and potential for broad dissemination. However, as with any study, the design has some constraints (Table 6).

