**Randomization**—After obtaining informed consent, participants will be assigned to Fit and Strong! or Fit and Strong! Plus using a randomized block design with blocks consisting of approximately 17 participants at each of the 3 sites. Within each block we will stratify by American College of Rheumatology (ACR) functional classes (I, II, or III) to achieve balance on arthritis severity by group. The random permutation of block sizes will help to minimize manipulation of an assignment.

**Inclusion/Exclusion Criteria**—*Inclusion criteria* include LE OA (hips, knees, ankles, feet, lower back), age 60+, no current participation in a regular exercise program, a calculated BMI of  $>=25 - 50 \text{ kg/m}^2$  (upper limit used in ORBIT) ([name] et al., 2010) and willingness to participate in measurement and intervention procedures. The study rheumatologist will examine participants at the baseline interview to confirm presence of LE OA and determine ACR functional class. *Exclusion criteria* include severe cardiovascular disease, active thrombophlebitis, recent pulmonary embolus, an acute systemic illness, poorly controlled diabetes, other health conditions that might preclude exercise training, age  $<60$ , current participation in organized PA, uncomplicated hip or knee surgery within the previous 6 months or complicated surgery within the past year, steroid injections in either knee or hip within the previous three months, or diagnosis of rheumatoid arthritis. Participants with blood pressure readings 180/110 mm Hg or higher or 90/50 mm Hg or lower will be excluded.

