**Intervention Instructors**—*Exercise instructors delivering the programs will be certified by at least 1 of 10 possible nationally recognized certification bodies* (e.g., ACSM, ACE, etc.). Certified exercise instructors (CEIs) will be trained separately to conduct either Fit and Strong! or Fit and Strong! Plus. The CEIs will lead exercise sessions, maintain participant attendance records, and negotiate participant adherence plans during week 6. They will also facilitate the group problem solving sessions (see Fit and Strong! Plus Instructor Manual in Appendix F). If both programs are offered at the same site on the same day, we will schedule one program in the morning and the other in the afternoon to minimize contact between both participants and instructors. An alternative will be to schedule one program Mon, Weds, Fri and the other Tues, Thurs, Sat. Instructors for customary Fit and Strong! will participate in *an 8-hour training protocol* that we developed and refined over multiple studies. The protocol reviews theories used to design Fit and Strong!, findings from completed research, along with detailed information and hands-on modeling of the exercise components (warm ups, flexibility, aerobic conditioning, strength training, cool down), role playing group problem solving processes, and negotiating PA contracts. Fit and Strong! Plus instructors will participate in *a 12-hour training protocol* for Fit and Strong! Plus that includes the full Fit and Strong! instructor training plus training on *diet and weight management*. The training will cover the *contribution of excess weight to disability and exacerbation of OA symptoms, the significance of a minimum 5% weight loss* for this population, components of a healthy diet, the new USDA my plate (choosemyplate.gov), food shopping on a budget, healthy meal preparation, handling situations that trigger impulse eating, tips for healthy eating at restaurants, ethnic eating, cultural aspects of eating preferences, and choosing foods at special occasions. **Drs. [name] and [name], both of whom participated in the pilot training, developed the draft protocol.** The protocol includes role play for facilitating diet-focused group discussion/problem solving sessions and negotiating *PA and diet adherence contracts* (see Instructor Training, Appendix G).

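### The analysis model has no term linking people taught in the same class, so the Plus*Time standard error is too small if change correlates within class; the plan gives no ICC, and the inflation is modest if class effects fade

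*Combined protocol and SAP*

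**What the plan says.** Both programs are delivered in groups, 24 sessions over 8 weeks (Completed Work). The Conceptual Model section names social modeling and group problem solving among the means of change. Under Intervention Instructors, "Certified exercise instructors (CEIs) will be trained separately to conduct either Fit and Strong! or Fit and Strong! Plus", so instructor is nested in arm.

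Allocation is of individuals, in "blocks consisting of approximately 17 participants at each of the 3 sites" (Randomization). The target sample is built as 2 interventions x 3 sites x 4 replications x 17 = 408.

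The Data Analysis section states that the design "consists of one between-participant effect (customary Fit and Strong! vs. Fit and Strong! Plus) and one within participant effect (time) variable". Its equation has fixed effects for Plus, Time, Plus*Time and ARA, a random effect for the person, and a last term that "is a person-time specific error term". The Plus*Time term "tells us whether the rate of change with respect to time is greater (or less) in the Plus condition". The error correlation is at first exchangeable: "However that assumption can be relaxed by using simple auto-regressive or Toeplitz (banded) correlation structures". The section adds that "by including properly coded dummy variables for discrete time, we can test more specific hypotheses regarding non-linear effects".

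Neither the analysis, missing-data nor power text contains a class or instructor term, a clustered standard error, a design effect or an ICC. Table 6 lists delivery by multiple instructors at multiple sites as a design consideration and answers it with fidelity monitoring.

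**The concern.** People who share a class share an instructor, a peer group and a timetable. If some classes change more than others for those reasons, classmates' changes are correlated. Each class belongs to one arm, so this variation enters the arm contrast directly. Individual randomisation does not remove it, because the dependence arises after allocation.

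Auto-regressive and Toeplitz structures describe repeated measures on one person and do not connect different people. The model would therefore count class-level variation as independent person-level noise. The Plus*Time standard error would be too small, confidence intervals too narrow and the two-sided error rate above its nominal level. How far depends on the ICC of change, which the plan does not give.

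**Working it through.** **Inputs from the plan.** 2 x 3 x 4 = 24 arm-by-site-by-replication cells of 17; visits at 0, 2, 6, 12 and 18 months; cross-time correlation .9; effect .2 SD at the end; 5% attrition per time point; power .9; about 300 needed, 400 enrolled.

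**Assumed.** Each cell is one class; alpha .05; all ICCs; unit variance with exchangeable correlation, so the residual variance is .1; a fading pattern of 1, .5, .25, .1 at months 2, 6, 12, 18.

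**The plan's 300.** The visits have mean 7.6 and sum of squared deviations S = 219.2. The variance of a person's slope is .1/219.2 = .000456, and the target slope difference is .2/18 = .0111. Without attrition, n per arm = 2 x 3.2415² x .000456/.0111² = 77.6, a total of 155. With 5% attrition per visit the total is 185 (actual spacing) or 198 (equal spacing). The 300 is not reproduced, but alpha and the correlation structure are not stated, so this does not show it to be wrong. The point does not depend on it.

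**Inflation.** Design effect DE = 1 + (17 - 1) x ICC. Actual type I error of a nominal 5% test = 2[1 - Φ(1.96/√DE)].

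*ICC defined on 2-month change.* The change variance within class is 2 x (1 - .9) = .2, so the class variance is .2 x ICC/(1 - ICC): .00408 at ICC .02 and .01053 at .05. A class effect with time pattern g adds to the slope a variance equal to the class variance times (Σ(t - 7.6)g/S)². The multiplier inside the square is .0347 if the effect stays flat and -.0194 if it fades.

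| Class effect after week 8 | ICC | Induced slope ICC | DE | Type I error |
|---|---|---|---|---|
| Fades | .02 | .0034 | 1.05 | 5.6% |
| Fades | .05 | .0086 | 1.14 | 6.6% |
| Stays flat | .02 | .0106 | 1.17 | 7.0% |
| Stays flat | .05 | .0270 | 1.43 | 10.1% |

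Simulation of the written model with dropout gave 6.1% (fading) and 9.8% (flat) at ICC .05, and 5.1% at ICC 0.

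*Class differences growing linearly to month 18.* The ICC then applies to the slope itself. At .02, DE = 1.32 and type I error is 8.8%; at .05, DE = 1.80 and it is 14.4% (simulated 8.2% and 13.5%).

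*Visit dummies.* Fading has not yet started at month 2, so the Plus-by-month-2 contrast has DE 1.32 and 1.80 and type I error 8.8% and 14.4% at ICC .02 and .05 (simulated 8.6% and 15.0%). At month 6, with half the class effect left, ICC .05 gives 7.5% (simulated 7.2%).

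**Which class-level test.** Both arms run in each site and replication, so trends shared by a site or season cancel in the arm contrast. I simulated slopes for 12 site-by-replication pairs (40,000 null runs, no dropout). With no class effect and a shared-trend ICC of .02 or .05, an unpaired class-level test on 22 df had type I error of about 2.5% and 1%. The paired test on 12 - 1 = 11 df stayed at about 5% throughout, including with class ICC .05.

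**Cost in precision and power.** The t quantile on 11 df is 2.201, and 2.201/1.960 = 1.12. Power at 400 uses noncentrality 3.2415 x √(400/N0)/√DE with a noncentral t on 11 df. With N0 = 300, the noncentrality is 3.74, 3.48 and 3.26 at class ICC 0, .01 and .02, giving power of about 93%, 89% and 84%. With N0 = 185 to 198 it is about 99%, 97-98% and 95-96%.

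**The case against.** The strongest reply is that this is a conditional omission of unknown size. The plan reports no correlation within classes, presents its equation as a basic model and does not rule out further terms. Classes end at week 8. After that, contact is by individual calls in months 4, 8 and 15 plus newsletters, so class effects may well fade, and the power target is the end of the study. This stands as to size: for the linear test, the fading case is the one to lead with. It does not remove the point. The listed extensions do not address clustering, secondary outcomes are to be compared at all time points, and Table 5 places efficacy at 2 and 6 months, where fading helps little.

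The class structure is also inferred. The Randomization section uses approximately 17 for a block, and the text just before the sample-size product was not available. That stands, and every figure above depends on it.

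A reader might infer that type I error is about 14%. For the linear test that needs class differences still growing to month 18 at slope ICC .05, which nothing in the plan suggests. A reader might also infer that the trial is underpowered. The plan does not support that either: the ICC is unknown, the 300 could not be reproduced, and 400 are enrolled.

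**Conclusion.** The point holds conditionally. The planned model cannot represent correlated change among classmates, and any such correlation makes the Plus*Time standard error too small. At assumed ICCs of .02 to .05 on 2-month change, the linear test's error rate is about 5.6-6.6% with fading class effects and 7.0-10.1% with persistent ones; month-2 contrasts are at about 9-15%. These figures rest on 24 classes of 17, exchangeable correlation of .9 and alpha .05. Whether the model also needs a person-level slope is a separate question and is not counted here. The point is worth fixing before analysis because the remedy needs no knowledge of the ICC.

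**What to change.** Pre-specify that the Plus*Time test and any visit contrasts allow for class-level clustering while respecting randomisation within site. One way is to include site-by-replication-by-time effects and base inference on the 12 paired class-level differences, with t on about 11 df. An equivalent is a mixed model with those effects, class-by-time random effects and small-sample df. If the classes as run differ from the inferred 24, use the actual ones.

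Two shortcuts should be avoided. A class random intercept alone is not enough, because a constant class shift cancels from within-person change. Class-robust standard errors on 22 df without the site-by-replication terms are conservative when sites or seasons share trends.

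State the planned number of instructors and record the instructor of each class. This is feasible: instructors "maintain participant attendance records" and Table 5 tracks instructor attrition. Report instructor-level clustering as a sensitivity analysis. As a mandatory primary test it could be expensive: with 6 instructors (assumed; 68 participants each, 4 df), power at 400 is about 80% at instructor ICC 0 and 59% at .01 on the 300 basis, or 92-94% and 76-78% on the 185-198 basis.

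State power at 400 over a stated ICC range. The cost is analysis work and SAP wording, intervals about 12% wider before any ICC, and a lower stated power. No design change is needed.

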**Table 3: Proposed Study Measures**

**A. Screening Measures**

10-item Short Portable Mental Status Questionnaire (Kahn et al., 1960)	
 
• Screens for moderate-to-severe cognitive impairment
 
• Good reliability and validity (Kane and Kane, 1981)
 
• Ineligible if answer more than three items incorrectly
 

Physical examination of joints and muscles by study rheumatologist	
 
• Determines clinical presence of OA in LE joints
 
• Rates functional significance using ACR arthritis functional class (Hochberg et al., American College of Rheumatology, 1992)
 

History of falls	
 
• Self-reported number of falls in last 2 years (Mobility and aging survey developed and used by the Centers for Disease Control and Prevention Healthy Aging Network).
 

B. Dependent Measures: Assessed at baseline, 2, 6, 12 and 18 months	
Primary Proximal Outcomes	
National Cancer Institute (NCI) Percent Energy from Fat Screener (Thompson et al., 1998)	
 
• Assesses usual daily intake from fat over previous 12 months
 
• Correlates strongly with true dietary intake (Thompson et al., 2007)
 

NCI Fruit and Vegetable Screener (Thompson et al., 2000)	
 
• Obtains fruit and vegetable intake during a typical day
 
• Correlates strongly with true dietary intake (Thompson, 2002)
 

Block Brief Food Frequency Questionnaire (FFQ) (Block et al., 1990)	
 
• Assesses 6-month changes in energy intake, % energy from fat, saturated fat, grams of fiber, servings of fruit and vegetables based on 70 food items
 
• Reliability and validity demonstrated in a wide range of age, gender, income and ethnic groups including low-income women (Coates et al., 1991; Block et al., 1992; Lanza et al., 2001; French et al., 2000)
 

Primary Distal Outcomes	
Weight and BMI	
 
• Weight measured without shoes using same calibrated Tanita BWB-800 digital scale
 
• Height measured without shoes to calculate BMI using Seca 214 portable stadiometer
 

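### The mixed model freely estimates a baseline arm difference that randomisation makes zero in expectation: valid, but a cheap, minor gain in precision is left unused

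*Combined protocol and SAP*

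**What the plan says.** The Data Analysis section introduces its equation with "The basic model for data analysis is" and lists free terms for Plus, Time and Plus by Time, a covariate labelled ARA, a person-level random effect and an error term. Plus "is a dummy variable for the Fit and Strong! Plus effect, relative to customary Fit and Strong". The product of Plus and Time "tells us whether the rate of change with respect to time is greater (or less) in the Plus condition". As written, time is linear and the structure is an exchangeable "correlation matrix among the errors". The same section allows a squared time term, dummy variables for discrete times, and autoregressive or banded correlation.

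Table 3 heads the dependent measures "Assessed at baseline, 2, 6, 12 and 18 months", so baseline is the first of five repeated measures. The Randomization section assigns participants at random in blocks, stratified by ACR functional class.

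I found no constraint making the baseline means equal, and no adjustment for the outcome's own baseline value. The adjustment variables named are ARA, the antecedents in the Conceptual Model (demographic, disease and functional class), and longitudinal covariates such as pain under Missing Data. Two stretches of the Approach section, either side of the conceptual model, were not in the text available to me, so this absence is established only for the rest.

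**The concern.** With time zero at baseline, the Plus coefficient is the arm difference before anyone has been treated. Random assignment makes its expected value zero. Estimating it anyway turns the treatment effect into a contrast of changes from baseline. When the correlation over time is below 1, that contrast subtracts the whole chance baseline difference, although only a fraction ρ of it is expected to persist. The excess is noise.

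At stake is precision. The section uses the secondary outcomes to ask whether adding diet helps, makes no difference or does harm, and Table 6 (item 5) keeps tests two-sided because the activity content was condensed. Those comparisons may have less power to spare than weight does.

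**Working it through.** **Inputs from the plan.** Visits at 0, 2, 6, 12 and 18 months; 1:1 allocation; correlation .9 for weight; 5% attrition per time point; effect .2 SD with a linear course; "Assuming a 2-tailed test"; about 300 participants needed to detect the effect "at the end of the study with power = .9"; 400 to be enrolled.

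**Assumed.** Time zero at baseline; alpha .05 (none is stated); unit SD; dropout compounding over four follow-ups (.95^4 = .81 remaining); correlations of .5 and .7 for secondary outcomes.

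**The plan's own figure.** N = (1.96 + 1.282)² × V / .2², where V is N times the generalised-least-squares variance of the effect. At exchangeable .9 with Plus free:
- slope, expressed over 18 months: V = .706, N = 185
- 18-month contrast: V = .934, N = 245

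Neither gives 300, which would need a correlation of about .84 to .88. That is a separate matter and does not affect the ratios below.

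**Formula without dropout, 18-month contrast.** Plus free: V = 8(1−ρ). Common baseline mean: V = 4(1−ρ²). Ratio = (1+ρ)/2, which is .95 at ρ = .9, .85 at .7 and .75 at .5.

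**With 5% dropout per visit.** The saving in V for the 18-month contrast is 4(1−r)², where r is the correlation between baseline and month 18: .04 at .9, .36 at .7 and 1.00 at .5. For AR(1) .9 across visits, r = .9^4 = .656 and the saving is .47.

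| Correlation | 18-month V, free → common baseline | Ratio | Slope ratio |
|---|---|---|---|
| Exchangeable .9 (plan, weight) | .934 → .894 | .957 | .975 |
| Exchangeable .7 (assumed) | 2.78 → 2.42 | .871 | .914 |
| Exchangeable .5 (assumed) | 4.60 → 3.60 | .783 | .834 |
| AR(1) .9 | 3.10 → 2.63 | .847 | .868 |

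**Power for weight at N = 400, effect .2 SD, exchangeable .9.** Slope 99.7% → 99.8%; 18-month contrast 98.5% → 98.8%.

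**Power for a secondary outcome at N = 400, effect .2 SD.**
- ρ = .7: slope 79% → 82%; 18-month contrast 67% → 73%
- ρ = .5: slope 57% → 65%; 18-month contrast 46% → 56%

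**Deleting Plus from the linear-time equation.** In that equation Plus is the intercept of a fitted line, so it also absorbs curvature. Fitted slope × 18 months, 5% dropout, ρ = .5:
- effect .067 SD at month 2, then .20 from month 6: free .192, constrained .214
- effect .15, .20, .12, .06 SD at the four follow-ups: free .007, constrained .051

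At ρ = .9 the constrained values are .194 and .012. The constrained slope therefore depends on the correlation as well as on the treatment effect.

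**The case against.** **Weight gains almost nothing.** At the only correlation the plan gives, the required N falls from 185 to 181 (slope) or from 245 to 235 (18-month contrast), and power at 400 moves by less than one point. This stands. The AR(1) row lowers the baseline to 18-month correlation to .66, which fits poorly with the plan's single figure of .9; autoregression is only a permitted relaxation. It marks a possibility, not the base case.

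**The larger gains rest on correlations outside the documents.** This also stands. A reader might infer that secondary outcomes certainly lose much more. The internal consistencies in Table 3 (.72 to .81 for anxiety, depression, stiffness and pain) make values below .9 plausible. But they do not measure stability over time, and physical function has .95. The range is conditional.

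**Two stronger readings fail.** A reader might infer that baseline data are discarded. They are not: baseline is in the outcome vector and is the reference for change, but it is used inefficiently. A reader might also infer bias. Over repeated randomisations there is none. In a single trial, a chance imbalance moves the 18-month contrast by (1−ρ) times its size, but that is the same imprecision already counted above.

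**The change is not free of conditions.** The constraint is safe only with time coded by visit, and the plan expects a 6-month weight loss that is then maintained, which is a plateau. This stands and shapes the fix.

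**Conclusion.** The concern holds as a minor efficiency point. The planned analysis is valid, and no conclusion about weight is threatened: at the plan's own exchangeable .9 the avoidable variance is 2.5% (slope) to 4% (18-month contrast), rising to 13-15% only if correlation decays as AR(1) .9. For secondary outcomes the avoidable variance is about 9-17% (slope) or 13-22% (18-month contrast) if their correlation is .5 to .7, which the documents neither support nor exclude.

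These figures assume time zero at baseline, 1:1 allocation and 5% compounding dropout; the power figures also assume alpha .05. A different origin for time would relabel the Plus coefficient but would still leave the baseline difference free.

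**What to change.** Code time by visit, which the Data Analysis section already allows. Then do one of the following:
- constrain the two arms to a common baseline mean, with separate arm differences at 2, 6, 12 and 18 months; or
- model only the post-baseline visits, with the baseline value of the outcome and its interaction with visit as covariates.

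Report the arm difference at each visit for weight and the secondary outcomes. This also defines the between-group differences at all time points that the section promises for secondary outcomes. Do not delete Plus while time stays linear.

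Confirm that each baseline measure is taken before assignment. The Procedures, Randomization and Inclusion/Exclusion sections imply this, since consent and the stratifying ACR class come from the baseline interview, but do not say it for every measure. Include height and weight borrowed from the ancillary study in that check.

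Cost: a few more parameters, no new data and the same software. One trade-off should be stated. If the course really is linear, an 18-month contrast is less precise than a slope: for weight, N = 235 with the common baseline against 185 for the planned slope. Both are well below 400.
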